#### **5.3.4** Handling of Withdrawals

Patients who discontinue the study drug will be encouraged to stay on study and will continue to be followed for safety and efficacy endpoints, unless they have withdrawn consent.

#### **5.3.5** Termination of Study

This study may be prematurely terminated if there is sufficient reasonable cause, including but not limited to:

- Unexpected, significant, or unacceptable risk to subjects
- Regulatory authorities decide that study should be terminated
- Insufficient compliance with protocol requirements
- Data are not sufficiently complete and/or not evaluable

## 6 STUDY INTERVENTION/INVESTIGATIONAL PRODUCT

## **6.1** Study Product Description

#### **6.1.1** Acquisition

Omnaris (aqueous nasal ciclesonide) and Alvesco (aerosol oral ciclesonide) will be supplied free of charge by Covis Pharma

#### **6.1.2** Formulation, Packaging, and Labeling

The study medicines will be packaged in GCP appropriate packaging/labelling by the Research Pharmacies at each of the approved provincial centers. RI-MUHC will do this for the province of Quebec. Dispensed medications will be delivered by courier (e.g. Fedex) to study participants directly from the research pharmacies in packaging which obscures the content. At the end of the treatment period, patients will be asked to safely dispose of their unused medication by going to the nearest pharmacy or ecocenter. Due to the COVID-

19 pandemic, pateints will not be allowed to send back their unsed medication to the study site due to risk of fomites.

#### **6.1.3 Drug Description:**

Drug name: [11 beta, 16 alpha (R)]-16, 17-[(Cyclohexylmethylene)-bis(oxy)]-11- hydroxy-21-(2-methyl-1-oxopropoxy) pregna-1,4-diene-3,20-dione

#### **6.1.4** Formulation:

Oral: 100 or 200mcg/actuation (ex-valve)

Nasal: 50mcg/metered spray

#### **6.1.5** Product Storage and Stability

Omnaris: Store at room temperature up to 30°C

Alvesco: Cannister contains pressurized liquid. Store at room temperature 15-25°C and protect from temperatures above 50°C. Do not freeze.

# 6.2 Dosage, Preparation, and Administration of Investigational Product

6.2.1 Drug/Device Handling: Omnaris (aqueous nasal ciclesonide) and Alvesco (aerosol oral ciclesonide) or placebo will be dispensed by the Research Pharmacy in each approved center. The RI-MUHC will do this for the province of Quebec. To do so, the study investigators will send a prescription to the Pharmacy, the pharmacy will dispense the appropriate study medicine. The medicine will then be provided to research volunteers via FedEx / courier delivery in the province of approval (e.g. within Quebec for RI-MUHC).

## **6.3** Modification of Investigational Product for a Participant

In the event of substantial side effects, participants may discontinue the study medication and stay in the study to complete follow up.

#### **6.4** Accountability Procedures for the Investigational Product:

Accountability will be via self-report at the day 14 virtual questionnaire.

[figure not shown]
## **6.5** Assessment of Subject Compliance

Adherence will be via self-report at day 14 virtual questionnaire.

#### **6.6** Concomitant Medications/Treatments

Participants may receive other concomitant medications or therapies and will be asked to report these in regard to other therapies received on day 1, 3, 5, 7, 10, 14 and in the event of hospitalization. Participants will be recommended not to continue the study drug if hospitalized.

# 7 STUDY SCHEDULE

- Information includes consent document. The patient signs electronically in the application after answering questions which confirm comprehension.
- If eligible, drug is prescribed, they are randomized, and shipping is arranged for study drug or placebo

Questionnaire	Day 0	Day1	Day 3	Day 5	Day 7	Day 10	Day 14	Day 29
Eligibility (screening form)	X							
Enrolment form (for eligible patients)	X							
Follow up questionnaire (MESA COVID 19)	X	X	X	X	X	X	X	X
Severity of overall symptoms	X	X	X	X	X	X	X	X
Dyspnea characteristics	X	X	X	X	X	X	X	X
Dyspnea severity	X	X	X	X	X	X	X	X
Visual analog scale for individual symptoms	X	X	Х	X	X	X	Х	X
Sleep PROMIS scale	X	X	X	X	X	X	X	X
Anxiety PROMIS scale	X	X	X	X	X	X	X	X

WHO ordinal scale	X	X	X	X	X	X	X	X
Hospitalization/Oxygen		X	X	X	X	X	X	X
use query								
Side effects query		X	X	X	X	X	X	X
Mortality							X	X
Subject orientation of							X	
the type of the study								
drug (placebo or active								
drug)								

# 7.1 Screening

- Baseline screening for eligibility through online questionnaire
- Informed consent by electronic consent form in REDCap
- Participant answers comprehension questions to ensure understands study protocol
- This will be performed via a web-based form. Eligibility criteria will be by self-report.

#### 7.2 Enrollment/Baseline

## **7.2.1** Randomization (Day 0)

- Medication list and screening form will be reviewed by central physician using the doctor review function in REDCap.
  - O If there are any doubts about the subject's appropriateness, the patient will be called by telephone to obtain more details. The medication list provided by the patient will be specifically reviewed by an expert physician in Internal Medicine who is aware of issues surrounding polypharmacy. Patients who have an unacceptable medical review will be excluded prior to randomization and the reason noted.
- Participants will be randomized by a computer-generated algorithm using a permuted block randomization sequence
- Randomization will be stratified by study site and sex
- Investigational pharmacy will dispense the masked study medicine
- Study personnel will then courier study medicine to the participant
- Participant will be sent an email about when to expect medication to arrive

#### 7.3 Follow-up

#### Day 0 Virtual questionnaire

• Query for symptom status

#### Day 1 Virtual questionnaire

- Verify receipt of study medicine
- Clinical status check-in
- Participant starts study medicine Ciclesonide 600mcg BID inhaled with aero chamber plus intranasal ciclesonide 200 mcg DIE

- Confirm the positive SARS-CoV-2 test result
- Query for symptom status
- Assess other medicines used during study period
- self reported hospitalization and oxygen use

#### Day 3, 5, 7, 10 Virtual questionnaires

- Clinical status check-in
- Query for symptom status
- Query for medication-related side effects / AEs
- Assess other medicines used during study period
- self reported hospitalization and oxygen use

#### **7.4** Final Study Visit

- Day 14 Visit
  - Clinical status check-in
    - Query for study medicine side effects since enrollment
    - Query for hospitalization or SAEs
  - Final outcome assessment
  - Completion of study medicine, which has a ~6-hour half-life
  - Assessment of adherence by self-report
  - Assess whether or not the patient believes they received study drug or placebo
  - Assess other medicines used during study period
- Day 29: Vital Status, clinical status, self reported hospitalization and oxygen use

#### **7.5** Early Termination Visit

If patients feel they are worsening they will need to see their healthcare providers to be medically assessed. They are to notify us via email or phone and case report forms will be generated. If patients are admitted to hospital, study drug will be stopped.

#### 7.6 Unscheduled/Sick Visit

Subjects will be provided a central email contact ([contact]). This is their central electronic point of contact and will be regularly responded to 7 days a week in a timely fashion. The person monitoring that account will either be a physician or will be someone who can contact a physician.

Patients will also receive phone numbers which will be manned but also have voicemail and will be responded to in a timely fashion.

All such interactions which may be due to coronavirus or a SAE will trigger a new daily CRF to be sent manually to log the patient's issue in the core dataset.

As this is a distance study, patients who are significantly unwell and who need urgent or emergent care will need to access regular channels for healthcare (e.g. doctors office, emergency room, etc.)

Additionally, those who have symptoms at baseline, or those who have developed NEW symptoms will be sent a follow-up eCRF on Day 10.

# 8 STUDY PROCEDURES/EVALUATIONS

#### **8.1** Clinical Evaluations

Clinical evaluations are by self-report

## **8.2** Laboratory Evaluations

There are no laboratory evaluations in the protocol.

SARS-CoV2 positivity is laboratory-confirmed and self-reported. Informed consent asks for access to medical records in case this needs to be verified.

Informed consent will request permission to contact local public health authorities or their medical provider in the event of loss to follow up or COVID-19 disease.

## **8.3** Subject Recruitment

- List of outpatients with COVID positive test will be contacted by research assistants by phone using script in appendix 3. They will ask patients for their email. If patients demonstrate interest in participation, research assistants will send them a link to study website. Study website has a link to REDCap portal for enrollment (www.containcovid19.com). Participants will only have data saved in REDCap. Research assistants will not enter any data from COVID list into REDCap.
- Flyers will be left at the testing center for interested participants to visit the study website. See appendix 4 for flyers

## **9** Assessment of Safety

## **9.1** Specification of Safety Parameters

Ciclesonide has a years-long track record of safety in Canada and the USA. As an already, Health Canada-approved medicine, this trial is designed as a pragmatic trial in the setting of a public health emergency.

# 9.2 Methods and Timing for Assessing, Recording, and Analyzing Safety Parameters

#### 9.2.1 Adverse Events

Minor Adverse events will not be captured, unless they result in hospitalization. See Serious Adverse Events below

Expected adverse events would include normal events within the general population as well COVID-19-related disease events which may include need for hospitalization, pneumonia, respiratory failure, sepsis, and death.

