Exclusion Criteria	
 
Already on inhaled corticosteroid medication
 
Currently using systemic steroids (oral or intravenous or intramuscular such as Prednisone) or use of steroids 7 days prior to enrolment
 
Severely ill patients at enrollment (i.e., admitted to ICU at admission)
 
Unable to self-administer the inhaler
 
Known or suspected pregnancy and breastfeeding
 
Known allergy to study medication or its components (non-medicinal ingredients; including lactose allergy (type I))
 
Patients with untreated fungal, bacterial or tubercular infections of the respiratory tract
 
Current hospitalization
 
Current use of oxygen at home or in hospital
 
Vaccinated for COVID-19
 

Stratification	Randomization will be stratified by sex
Statistical Assumptions	With 159 subjects per arm we will be able to detect an absolute increase of 15% in the number of patients with resolved symptoms at day 7.
Safety	Safety of the intervention will be assessed by the cumulative incidence of Grade 3 and 4 AE and SAEs using the Division of AIDS Table for Grading Severity of Adult and Pediatric Adverse Events version 2.1

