#### 2.2 Rationale

Current standard of care is supportive care after the diagnosis of COVID-19.

Ciclesonide is a corticosteroid currently used for asthma (in its inhaled form) and nasal rhinitis (in its spray form). It has a very good safety profile. Much higher doses of ciclesonide (up to a single inhalation of 3200 mcg) have been administered to healthy volunteers and were well tolerated (9). As such, inhaled and nasal ciclesonide at the doses of 600mcg BID for 2 weeks will have few adverse events. The usual doses for ciclesonide are:

Standard asthma treatment (ciclesonide, *Alvesco*):

- The recommended dose range for ciclesonide in inhalation is 100 to 800 mcg daily (9).
- The recommended starting dose for most asthmatic patients is 200 mcg daily in Canada (10).
- The maximum dose of 800 mcg daily should be administered as 400 mcg twice daily (9).

Standard allergic rhinitis treatment (ciclesonide, *Omnaris*) (11):

- The recommended dose of OMNARIS is 200 mcg per day administered as 2 sprays (50 mcg/spray) in each nostril once daily.
- The maximum total daily dosage should not exceed 2 sprays in each nostril (200 mcg/day)

As the specific dose of ciclesonide to decrease SARS-CoV-2 is unknown, we planned to give a higher dose than the maximum approved dose for asthma of inhaled ciclesonide (1200 mcg daily administered as 600 mcg twice daily) plus the usual dose of intranasal ciclesonide (200 mcg/day) for 14 days. Given viral replication begins in the nasal cavity and then progress to the lungs, we have chosen to administer ciclesonide both intranasally and inhaled. This dose has been chosen in order to maximize deposition of the study drug in the lower airways. Although the usual dose of ciclesonide for asthma is 400 mcg twice daily (for a total of 800 mcg/day), single doses (up to 3200 mcg) have been administered to healthy subjects without significant side effects (9).

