#### **9.2.3** Serious Adverse Events (SAEs)

SAEs (e.g. hospitalization) will be followed for up to 29 days to assess final outcome.

A patient who reports hospitalization and/or an adverse effect of the study drug on a CRF who has not reached out to the team by phone or email will be contacted in a timely fashion and the site doctor made aware. We will review the "positive" CRFs to detect these. We also collect details about the hospitalization.

Patients who do not complete their day 14 CRF will receive reminder emails and, if they do not respond to that, they will be telephoned. Patients must provide an alternate contact at enrollment. If they do not respond to the above means, we will call that contact to find out what has happened. If that person does not know or is not available, we will send registered mail to the address of the patient before concluding loss to follow-up. A sensitivity analysis of the mortality outcome will be performed assuming patients lost to follow-up despite these means have died.

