# **9.3** Reporting Procedures

#### **9.3.1** Serious Adverse Events

An AE or suspected adverse reaction is considered a serious adverse event (SAE) if it results in any of the following outcomes:

- Death
- life-threatening adverse event (as below),
- Hospitalization
- Persistent or significant incapacity or substantial disruption of the ability to conduct normal life functions, or
- Important medical events that may not result in death, but are life-threatening, or require hospitalizations may be considered serious when, based upon appropriate medical judgment they may jeopardize the patient or subject and may require medical or surgical intervention to prevent one of the outcomes listed in this definition.

Examples of such medical events include allergic bronchospasm requiring intensive treatment in an emergency room or at home, blood dyscrasias or convulsions that do not result in inpatient hospitalization, or the development of drug dependency or drug abuse.

Life-threatening adverse events: An AE is considered "life-threatening" if, in the view of either the site principal investigator or sponsor, its occurrence places the patient or subject at immediate risk of death. It does not include an AE that, had it occurred in a more severe form, might have caused death. For life threatening AEs, subjects would be recommended /expected to be hospitalized.

Based on the known safety track record of ciclesonide, this pragmatic protocol will focus on death, life-threatening AEs, and hospitalizations. Incapacity / permanent disability is a possibility with COVID-19, but this is not associated with ciclesonide. In the event of incapacity, the subject would be expected to be hospitalized.

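### The protocol gives conflicting rules on which adverse events are recorded, and Section 11.4 plans no by-arm safety analysis beyond hospitalization and mortality

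*Combined protocol and SAP*

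**What the plan says.** The protocol describes adverse-event recording in several places.

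- **Section 9.2.1:** "Minor Adverse events will not be captured, unless they result in hospitalization". It does not define minor.
- **Section 7, schedule table:** a row labelled "Side effects query" is marked at Days 1, 3, 5, 7, 10, 14 and 29.
- **Section 7.3, Days 3 to 10:** "Query for medication-related side effects / AEs". **Section 7.4, Day 14:** "Query for study medicine side effects since enrollment". The text for Day 1 and for Day 29 lists no such question.
- **Section 9.2.3:** "A patient who reports hospitalization and/or an adverse effect of the study drug on a CRF" is to be contacted if they have not already been in touch, and the site doctor is informed.
- **Section 9.3.1:** "this pragmatic protocol will focus on death, life-threatening AEs, and hospitalizations".
- **Summary, Safety row:** "Safety of the intervention will be assessed by the cumulative incidence of Grade 3 and 4 AE and SAEs", graded with the Division of AIDS table.

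Section 11.4 gives binomial regression for the primary and secondary outcomes, a Kaplan-Meier plot for time to resolution, and rules for withdrawals. Hospitalization and mortality are among the secondary outcomes in Section 3.2.2. Section 11.4 does not mention adverse events or side effects.

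On the inhaled dose, Section 2.2 says: "we planned to give a higher dose than the maximum approved dose for asthma of inhaled ciclesonide".

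**The concern.** A data manager cannot follow both Section 9.2.1 and the schedule. One says that milder events are not recorded; the other asks about them repeatedly. The Summary adds a third standard (Grade 3-4 AEs and SAEs), and Section 9.3.1 a fourth, narrower focus. None of these has an analysis method in Section 11.

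The gap matters most for lower-grade local effects. Section 2.3.1 lists such effects for ciclesonide: paradoxical bronchospasm 1.6%, dysphonia 1.0%, oral candidiasis 0.6%, throat irritation 0.3%. Most of these would not be expected to lead to admission, so outcomes built on admission or death would largely miss them. Section 2.2 expects few adverse events over two weeks and supports this with single doses given to healthy volunteers. The randomised comparison could test that expectation in the trial's own population, and the question is already scheduled. In mild outpatient disease with a Day 7 symptom endpoint, tolerability is a natural part of what a positive result has to be weighed against.

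**Working it through.** **Step 1. Compare the sections.**

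| Place | What is recorded or assessed | By-arm analysis in Section 11 |
|---|---|---|
| Summary | Grade 3-4 AEs and SAEs | None |
| Section 7 table | Side effects, 7 of 7 post-baseline forms | None |
| Sections 7.3-7.4 text | Side effects, 5 of 7 forms (Days 3, 5, 7, 10, 14) | None |
| Section 9.2.1 | Minor events left out unless they lead to admission | None |
| Section 9.2.3 | Positive answers reviewed and followed up | None |
| Section 9.3.1 | Deaths, life-threatening events, admissions | Hospitalization and mortality only, as secondary outcomes |

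Two gaps follow. Side effects below Grade 3 have neither a consistent recording rule nor an analysis. The Summary's Grade 3-4 endpoint has no capture, grading or analysis procedure in Sections 9 or 11.

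**Step 2. Reproduce the sample size, which fixes the available precision.** Inputs from Section 11.2: 65% versus 80%, 80% power, 5% alpha (sidedness not stated; two-sided reproduces the figure).

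n = [1.96·√(2p̄q̄) + 0.8416·√(p₁q₁ + p₂q₂)]² / (p₂ − p₁)², with p̄ the mean of the two rates.

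With p̄ = 0.725: [1.96·√0.39875 + 0.8416·√0.3875]² / 0.15² = 1.7616² / 0.0225 = 137.9, so 138 per arm and 276 in total. Then 138 × 1.15 = 158.7, so 159 per arm and 318 in total. Both match the plan.

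**Step 3. What 159 per arm could show for tolerability.** Same formula, solved for the active-arm rate that gives 80% power.

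- Comparator 1.6% (the labelled bronchospasm rate, used as an assumed placebo rate): active-arm rate about 8.5%. Check at 0.016 versus 0.0845: [1.96·√0.09545 + 0.8416·√0.09310]² / 0.0685² = 0.8623² / 0.004692 ≈ 158.5.
- Comparator 5% (assumed; no source in the documents): about 14.3%. Check at 0.05 versus 0.1425: [1.96·√0.17397 + 0.8416·√0.16969]² / 0.0925² = 1.1642² / 0.008556 ≈ 158.4.
- Equal rates of 1.6%: 95% CI half-width for the risk difference = 1.96·√(2 × 0.016 × 0.984 / 159) = 0.0276, or 2.8 points.
- No event of a given type in 159: one-sided 95% upper bound = 1 − 0.05^(1/159) = 1.9%.

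**Step 4. Allow for dropout.** With 15% lost, 159 × 0.85 ≈ 135 per arm. The detectable rates become about 9.4% versus 1.6% and 15.3% versus 5%, and the zero-event bound becomes 1 − 0.05^(1/135) = 2.2%.

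**Step 5. Dose description.** Section 2.2 gives 1200 mcg/day planned against an 800 mcg/day maximum; 1200/800 = 1.5. Section 9.3.2 calls the dosing standard. These two statements need reconciling. No view is taken here on the dose.

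**The case against.** The strongest defence is that this is a deliberately pragmatic trial of a marketed drug. Section 9.3.1 says that it concentrates on the gravest events. Those are largely covered, because hospitalization and mortality are compared by arm and the Summary adds Grade 3-4 AEs and SAEs. The conflict could also be settled by clarifying what captured means. Much of this stands, and it rules out several stronger readings that a reader might infer.

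- **That the side-effect answers are discarded.** The documents do not say so. Answers go into REDCap, positive forms are followed up, and Section 16 promises release of de-identified data. What is missing is a consistent recording rule and an analysis.
- **That nothing short of admission counts.** Section 9.2.1 leaves out only minor events. The Summary's Grade 3-4 endpoint does not require admission, and the SAE examples in Section 9.3.1 include bronchospasm treated intensively in an emergency room or at home.
- **That harm is not assessed at all.** Hospitalization and mortality are secondary outcomes with an analysis.
- **That the chance of seeing a case measures the lost comparison.** At 1.6%, 1 − 0.984^159 = 0.92, but this is the chance of at least one case in one arm with no dropout. It does not show that the arms could be separated. Step 3 is the relevant measure, and it is modest.

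Two practical limits also stand. The questionnaire is not reproduced, so it is unknown whether the question is yes/no, a checklist or free text. Section 9.5 reports in the past tense that the DSMB met at half enrolment and again when enrolment fell off, so a rule written now may be partly retrospective and 318 may not be reached.

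The defence does not remove the contradiction. A pragmatic focus on grave events does not explain why the forms ask about milder ones, nor why the Summary's endpoint has no method.

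**Conclusion.** The point holds in this limited form and should be corrected. The sections disagree on which adverse events are recorded. Section 11.4 has no safety analysis beyond two secondary outcomes, and the Summary's safety endpoint is not carried forward. If Section 9.2.1 is followed as written, lower-grade local effects get no by-arm result although the question is already scheduled.

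The loss is moderate. A by-arm table could detect a common effect or a large excess, and it would say little about rare effects at labelled rates. These figures rest on two-sided 5% alpha, equal arms, 159 per arm with no dropout (135 shown as the alternative), and placebo rates that are assumptions: labelled rates come from treated patients in another setting. That the query is on every follow-up form rests on the schedule table alone for Days 1 and 29. The primary analysis and the sample size are unaffected.

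**What to change.** 1. Reconcile the Summary, the Section 7 table, Sections 7.3 and 7.4 (including Days 1 and 29), and Sections 9.2.1, 9.2.3 and 9.3.1, so that they state one recording rule. Reconcile Sections 2.2 and 9.3.2 on how the dose is described.
2. Remove the sentence in 9.2.1 and state that all answers to the scheduled side-effect query are recorded. Say who applies the Division of AIDS grades to self-reported events, and from what information.
3. Add to Section 11.4 one table by arm, in all participants who took at least one dose, with risk differences and 95% confidence intervals for:
   - any reported side effect;
   - the local effects listed in Section 2.3.1, as far as the form allows;
   - Grade 3-4 AEs;
   - SAEs;
   - stopping study medication for a side effect (Section 6.3 permits this, but no count is planned).

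   Give the number who answered at least one side-effect query, since some dosed participants may return no form.
4. Present the intervals as descriptive, and label the table as specified late if it is added after enrolment has largely finished.

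The cost is protocol and analysis wording, one table, and the coding of answers. No new visit, question or participant is needed. If the form turns out to be yes/no only, or does not record the reason for stopping, the affected rows cannot be filled and the plan should say so.
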